5.10 Volume of blood

The total volume of blood that will be drawn from each patient for this study is listed in Table 4 and Table 5 as below. The collection of additional samples is performed locally at the discretion of the investigator and recorded in the eCRF as appropriate, thus requiring additional sample volumes.

	screening and open-label initial phase											
Assessment	Sample Volume	Numbe	r of Sample	Maximum blood volume Total (mL)								
	(mL)	V1	V 3 (D 1 ⁷)	V 4 (D 2 ⁷)	Rand (D 2/3 ^{7,8})	EOS (D 9 ⁷)						
Hematology	2		1 ³		0-1 ⁵	1	6					
Clinical Chemistry	8.5		1 ^{3,6}		0-1 ^{5,6}	1 ⁶	25.5					
Potassium (Central Lab S-K)	2.5		4-5 ^{2,6}	2^4			17.5					

Table 4Volume of blood to be withdrawn from each patient: optional pre-
screening and open-label initial phase

Table 4

Assessment	Sample Volume	Number	Maximum blood volume Total (mL)				
135055110110	(mL)	V1	V 3 (D 1 ⁷)	V 4 (D 2 ⁷)	Rand (D 2/3 ^{7,8})	EOS (D 9 ⁷)	
Potassium (i-STAT)	1	1 ¹	5-6 ²	24	1	1	11
Maximum Blood Volume Total (mL)		1	29	7	11.5	11.5	60

Volume of blood to be withdrawn from each patient: optional prescreening and open-label initial phase

V= Visit; D=Day

1. Blood potassium will be measured only by i-STAT at the optional Pre-screening visit (Visit 1).

Potassium will be measured twice 60 (±10) minutes apart within 1 day of first dose administration on the open-label initial phase Day 1(Visit 3) and at 1,2 and 4 hours (±15 min) after administration of the first dose of ZS; An extra potassium will be measured at 90 minutes (±15 minutes) after taking the second dose for patients with i-STAT potassium ≥ 6.1 or < 4.0 mmol/L at the 4 hour post Dose 1.

3. On the open-label initial phase Day 1(Visit 3), the Central Laboratory clinical chemistry and hematology samples will be collected at the same time as the 60 minutes i-STAT screening potassium sample.

4. Potassium will be measured predose (0 hour) and 1 hour (±15 min) post 1st dose on the open-label initial phase Day 2 (Visit 4), for those achieving normokalemia based on the predose i-STAT potassium value, they will then enter the randomized phase directly.

5. Clinical chemistry and hematology samples only for patients with i-STAT potassium values >5.0 mmol/L as measured fasting on the open-label initial phase Day 3.

6. Central laboratory S-K sample collected as part of the serum clinical chemistry

7. Study Day in Table 4 is day for the open-label initial phase.

8. Randomization Visit may occur for patients who achieve normokalemia on open-label initial phase Day 2 or 3.

Table 5Volume of blood to be withdrawn from each patient: 28-day randomized
treatment study phase

Assessment	Sample Volume (mL)	Numb	er of S	amples									Maxi mum blood volu me Total (mL)
		Rand D1 ²	V6 D2 ²	V7 D5 ²	V8 D8 ²	V9 D12 ²	V10 D15 ²	V11 D19 ²	V12 D22 ²	V13 D26 ²	V14 D29 ²	EOS D35 ²	
Hematology	2	1					1				1	1	8
Clinical Chemistry	8.5	1^1					1^{1}				1^{1}	1^1	34

Assessment	Sample Volume (mL)	ume											Maxi mum blood volu me Total (mL)
		Rand D1 ²	V6 D2 ²	V7 D5 ²	V8 D8 ²	V9 D12 ²	V10 D15 ²	V11 D19 ²	V12 D22 ²	V13 D26 ²	V14 D29 ²	EOS D35 ²	
Potassium (Central Lab S-K ¹)	2.5		1	1	1	1		1	1	1			17.5
Potassium (i- STAT)	1	1	1	1	1	1	1	1	1	1	1	1	11
Maximum Blood Volume Total (mL)		11.5	3.5	3.5	3.5	3.5	11.5	3.5	3.5	3.5	11.5	11.5	70.5

Table 5Volume of blood to be withdrawn from each patient: 28-day randomized
treatment study phase

V=Visit; D=Day

1. Potassium will be measured fasting prior to the daily dose. Central Laboratory S-K sample collected as part of the serum clinical chemistry at Day 1, 15, 29, and 35.

2. Study Day in Table 5 is day for the 28-day randomized treatment study phase.

5.11 Guidance related to assessments, and procedures during COVID-19 pandemic

In view of the ongoing and emerging novel coronavirus (COVID-19) pandemic spreading worldwide, the safety and well-being of our study participants is of primary importance. To protect the safety and well-being of study participants, Appendix C will provide guidance on the assessments and procedures during this period.

6. SAFETY REPORTING AND MEDICAL MANAGEMENT

The Principal Investigator is responsible for ensuring that all staff involved in the study are familiar with the content of this section.

6.1 Definition of adverse events

An adverse event is the development of any untoward medical occurrence in a subject or clinical study subject administered a medicinal product and which does not necessarily have a causal relationship with this treatment. An AE can therefore be any unfavourable and unintended sign (e.g., an abnormal laboratory finding), symptom (for example nausea, chest pain), or disease temporally associated with the use of a medicinal product, whether or not considered related to the medicinal product.

The term AE is used to include both serious and non-serious AEs and can include a deterioration of a pre-existing medical occurrence. An AE may occur at any time, including run-in or washout periods, even if no Study treatment has been administered.

6.2 Definitions of serious adverse event

A serious adverse event is an AE occurring during any study phase, that fulfils one or more of the following criteria:

- Results in death
- Is immediately life-threatening
- Requires in-patient hospitalization or prolongation of existing hospitalization
- Results in persistent or significant disability/incapacity
- Is a congenital abnormality or birth defect
- Is an important medical event that may jeopardize the patient or may require medical intervention to prevent one of the outcomes listed above

Adverse Events (AEs) for malignant tumours reported during a study should generally be assessed as Serious AEs. If no other seriousness criteria apply, the 'Important Medical Event' criterion should be used. In certain situations, however, medical judgement on an individual event basis should be applied to clarify that the malignant tumour event should be assessed and reported as a Non-Serious AE. For example, if the tumour is included as medical history and progression occurs during the study, but the progression does not change treatment and/or prognosis of the malignant tumour, the AE may not fulfill the attributes for being assessed as Serious, although reporting of the progression of the malignant tumor as an AE is valid and should occur. Also, some types of malignant tumours, which do not spread remotely after a routine treatment that does not require hospitalization, may be assessed as Non-Serious; examples include Stage 1 basal cell carcinoma and Stage 1A1 cervical cancer removed via cone biopsy.

For further guidance on the definition of a SAE, see Appendix A to Clinical Study Protocol

6.3 Recording of adverse events

6.3.1 Time period for collection of adverse events

Adverse Events will be collected from the time of main study informed consent, throughout the treatment period and including the EOS visit. SAEs will be collected from the time of optional Pre-screening informed consent, throughout the treatment period and including the EOS visit.

6.3.2 Follow-up of unresolved adverse events

Any AEs that are unresolved at the patient's last AE assessment (EOS) or other assessment/visit as appropriate in the study are followed up by the Investigator for as long as medically indicated, but without further recording in the eCRF. AstraZeneca retains the right to request additional information for any patient with ongoing AE(s)/SAE(s) at the end of the study, if judged necessary.

6.3.3 Variables

The following variables will be collect for each AE:

- AE (verbatim)
- The date when the AE started and stopped
- Maximum intensity (mild, moderate or severe)
- Whether the AE is serious or not
- Investigator causality rating against the Investigational Product (yes or no)
- Action taken with regard to investigational product
- Outcome

In addition, the following variables will be collected for SAEs:

- Date AE met criteria for serious AE
- Date Investigator became aware of serious AE
- AE is serious due to
- Date of hospitalization
- Date of discharge
- Probable cause of death

- Date of death
- Autopsy performed
- Causality assessment in relation to Study procedure(s)
- Description of AE

It is important to distinguish between serious and severe AEs. Severity is a measure of intensity whereas seriousness is defined by the criteria in Section 6.2. An AE of severe intensity need not necessarily be considered serious. For example, nausea that persists for several hours may be considered severe nausea, but not a SAE unless it meets the criteria shown in Section 6.2. On the other hand, a stroke that results in only a limited degree of disability may be considered a mild stroke but would be a SAE when it satisfies the criteria shown in Section 6.2.

6.3.4 Causality collection

The Investigator will assess causal relationship between Investigational Product and each Adverse Event, and answer 'yes' or 'no' to the question 'Do you consider that there is a reasonable possibility that the event may have been caused by the investigational product?'

For SAEs causal relationship will also be assessed for other medication and study procedures. Note that for SAEs that could be associated with any study procedure the causal relationship is implied as 'yes'.

A guide to the interpretation of the causality question is found in Appendix A to the Clinical Study Protocol.

6.3.5 Adverse events based on signs and symptoms

All AEs spontaneously reported by the patient or care provider or reported in response to the open question from the study personnel: 'Have you had any health problems since the previous visit?', or revealed by observation will be collected and recorded in the eCRF. When collecting AEs, the recording of diagnoses is preferred (when possible) to recording a list of signs and symptoms. However, if a diagnosis is known and there are other signs or symptoms that are not generally part of the diagnosis, the diagnosis and each sign or symptom will be recorded separately.

6.3.6 Adverse events based on examinations and tests

The results from protocol mandated laboratory tests and vital signs will be summarised in the clinical study report. Deterioration as compared to baseline in protocol-mandated laboratory values, vital signs should therefore only be reported as AEs if they fulfil any of the SAE criteria or are the reason for discontinuation of treatment with the investigational product.

If deterioration in a laboratory value/vital sign is associated with clinical signs and symptoms, the sign or symptom will be reported as an AE and the associated laboratory result/vital sign

will be considered as additional information. Wherever possible the reporting Investigator uses the clinical, rather than the laboratory term (e.g., anaemia versus low haemoglobin value). In the absence of clinical signs or symptoms, clinically relevant deteriorations in non-mandated parameters should be reported as AE(s).

Any new or aggravated clinically relevant abnormal medical finding at a physical examination as compared with the baseline assessment will be reported as an AE.

6.4 **Reporting of serious adverse events**

All SAEs have to be reported, whether or not considered causally related to the investigational product, or to the study procedure(s). All SAEs will be recorded in the CRF.

If any SAE occurs in the course of the study, then Investigators or other site personnel inform the appropriate AstraZeneca representatives within one day i.e., immediately but **no later than 24 hours** of when he or she becomes aware of it.

The designated AstraZeneca representative works with the Investigator to ensure that all the necessary information is provided to the AstraZeneca Patient Safety data entry site within 1 calendar day of initial receipt for fatal and life threatening events and within 5 calendar days of initial receipt for all other SAEs.

For fatal or life-threatening adverse events where important or relevant information is missing, active follow-up is undertaken immediately. Investigators or other site personnel inform AstraZeneca representatives of any follow-up information on a previously reported SAE within one calendar day i.e., immediately but **no later than 24 hours** of when he or she becomes aware of it.

Once the Investigators or other site personnel indicate an AE is serious in the WBDC system, an automated email alert is sent to the designated AstraZeneca representative.

If the WBDC system is not available, then the Investigator or other study site personnel reports a SAE to the appropriate AstraZeneca representative by telephone.

The AstraZeneca representative will advise the Investigator/study site personnel how to proceed.

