1.3.2 Clinical risks

The safety of ZS was evaluated in clinical trials for the reduction of hyperkalemia involving over 1,500 patients.

The most commonly reported adverse reaction was edema related events which were reported by 5.7% ZS patients; 1.7, 2.7, 5.2, and 14.3% of patients randomized to placebo, ZS 5 g, 10 g, or 15 g once daily up to one month, respectively. Fifty-three percent were managed with initiating a diuretic or adjusting a diuretic dose; the remainder did not require treatment.

In clinical trials, 4.1% of ZS patients developed hypokalemia with a serum potassium value less than 3.5 mmol/L, which was resolved with dose adjustment or discontinuation of ZS.

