If a patient develops i-STAT potassium values between 3.0 mmol/L and 3.4 mmol/L, inclusive (confirmed by taking a second potassium measurement after a 10 ± 2 minute interval), during the 28-day randomized treatment study phase, dosing will be reduced from qd to qod for the remainder of the study.

Patients with confirmed potassium <3.0 mmol/L in both study phases should discontinue from therapy as per Section 3.9.

Patients with confirmed i-STAT potassium >6.2 mmol/L during the 28-day randomized treatment study phase should discontinue from therapy as per Section 3.9.

For doses administered in the clinic during both study phases each dose will be individually dispensed by designated, trained site staff.

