7.7 Concomitant and other treatments

All concomitant medications taken by the patient from 7 days prior to the open-label initial phase Day 1 until the 28-day randomized treatment study phase Day 35(EOS), or the end of the study (7 ± 1 days after the last dose of IP) for patients, will be recorded.

Whenever possible, all blood draws collected prior to meals should be collected prior to any insulin/insulin analog treatment. From the open-label initial phase Day 1 through the 28-day randomized treatment study phase Day 28, the time of dosing with insulin/insulin analogs must be recorded when IP is administered in the clinic.

During the study, the patient cannot receive alternative treatment for hyperkalemia while taking IP. If dosing with IP is discontinued or the patient has completed dosing, the patient may receive alternative treatment for hyperkalemia if clinically indicated prior to completing the EOS visit. Any alternative treatment administered after the end of IP administration and prior to the EOS visit must be recorded in the concomitant medication eCRF page (and as AE if applicable).

In addition to therapies for hyperkalemia also other drugs with World Health Organization Anatomic Therapeutic Chemical classification code V03AE, i.e., potassium binders such as sevelamer, calcium acetate, and lanthanum carbonate, are prohibited to be taken while receiving IP, as the effects of potassium binding drugs may effect safety laboratory assessments.

Changes to RAAS inhibitor and/or diuretics (including adding a new, changing the dose or discontinuation or switching of RAAS inhibitor and/or diuretics) during the study are prohibited. If clinically indicated to change the RAAS inhibitor and/or diuretics, the patients should discontinue study medication.

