- Consistency with known drug profile. Was the AE consistent with the previous knowledge of the suspect drug (pharmacology and toxicology) or drugs of the same pharmacological class? Or could the AE be anticipated from its pharmacological properties?
- De-challenge experience. Did the AE resolve or improve on stopping or reducing the dose of the suspect drug?
- No alternative cause. The AE cannot be reasonably explained by another aetiology such as the underlying disease, other drugs, other host or environmental factors.
- Re-challenge experience. Did the AE reoccur if the suspected drug was reintroduced after having been stopped? AstraZeneca would not normally recommend or support a re-challenge.
- Laboratory tests. A specific laboratory investigation (if performed) has confirmed the relationship.

In difficult cases, other factors could be considered such as:

- Is this a recognized feature of overdose of the drug?
- Is there a known mechanism?

Causality of 'related' is made if following a review of the relevant data, there is evidence for a 'reasonable possibility' of a causal relationship for the individual case. The expression 'reasonable possibility' of a causal relationship is meant to convey, in general, that there are facts (evidence) or arguments to suggest a causal relationship.

The causality assessment is performed based on the available data including enough information to make an informed judgment. With limited or insufficient information in the case, it is likely that the event(s) will be assessed as 'not related'.

Causal relationship in cases where the disease under study has deteriorated due to lack of effect should be classified as no reasonable possibility.

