4.3.2.2 Presentation

Adverse Events will be presented separately for the OLP and the RTP. The analyses will mainly be focused on on-treatment AEs, but some tables will be replicated for all AEs occurring during a study period. All adverse events will be summarized by SOC and PT. All AEs, including those not considered on-treatment, will be included in safety listings but excluded from the summary tables.

The onset date of the AE determines the phase in which the AE will be summarized. This is in order to have a consistent "worst case" allocation of AEs, because it will not be possible to distinguish AEs occurring before or after the actual intake of randomized IP.

Overall Summary of Adverse Events

AEs will be summarised by treatment group for the OLP and RTP and will include the following:

- the number and percentage of subjects experiencing an AE
- the number and percentage of subjects experiencing an AE with an outcome of death
- the number and percentage of subjects experiencing a SAE
- the number and percentage of subjects experiencing an AE leading to treatment withdrawal

This table will be done both on-treatment and using all AEs that occurred during RTP.

AEs and SAEs by System Organ Class (SOC) and Preferred Term (PT)

The number and percentage of subjects with AEs and SAEs will be summarised by SOC and PT, by treatment group. A subject with more than one type of AE in a particular SOC will be counted only once in the total of subjects experiencing AEs in that particular SOC. Since a subject could have more than one type of AE within a particular SOC, the sum of subjects experiencing different AEs within the SOC could be larger than the total number of subjects experiencing AEs in that SOC. Similarly, a subject who has experienced an AE in more than one SOC will be counted only once in the total number of subjects experiencing AEs in all SOCs.

AEs by PT and frequency

The number and percentage of subjects with AEs will be summarised by PT and treatment group and sorted by descending frequency on PT level.

Possibly related AEs and SAEs by SOC and PT

The number and percentage of subjects with possibly related AEs and SAEs will be summarised by SOC, PT, and treatment group.

AEs by SOC, PT, and maximum severity

The number and percentage of subjects with AEs will be summarised by SOC, PT and maximum intensity, and treatment group.

Deaths

The number and percentage of subjects with SAEs or AEs with outcome of death will be

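### Most stops for potassium >6.2 mmol/L enter the AE-withdrawal row, and no planned table separates them by arm from other AE withdrawals

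*Protocol*

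**What the plan says.** - **AE rule (protocol 6.3.6).** It concerns "Deterioration as compared to baseline in protocol-mandated laboratory values, vital signs", and says these "should therefore only be reported as AEs if they fulfil any of the SAE criteria or are the reason for discontinuation of treatment with" study drug. It does not name the baseline.
- **Stopping rules (protocol 7.2).** "Patients with confirmed i-STAT potassium >6.2 mmol/L during the 28-day randomized treatment study phase should discontinue from therapy as per Section 3.9". For low values: "Patients with confirmed potassium <3.0 mmol/L in both study phases should discontinue from therapy as per Section 3.9". Section 3.9 lists this potassium criterion and adverse events as separate entries.
- **Causality (protocol Appendix A).** "Causal relationship in cases where the disease under study has deteriorated due to lack of effect should be classified as no reasonable possibility".
- **Withdrawal row (SAP 4.3.2.2).** The overall AE summary gives, by arm, "the number and percentage of subjects experiencing an AE leading to treatment withdrawal". It is produced for on-treatment AEs and again for all randomized-phase AEs. The other AE tables (system organ class and preferred term, frequency, severity, relatedness) cover all AEs, not those leading to withdrawal.
- **Efficacy use of the same stops (SAP 4.2.3.2).** A randomized-phase discontinuation for high potassium counts as a hyperkalemia event. (The parenthesis there names a blood draw that protocol 4.3.1 places in the open-label phase, but the sentence is about randomized-phase stops.)
- **Coding (SAP 4.3.2.1).** Hypokalemia is taken from laboratory values and is excluded from MedDRA coding.

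**The concern.** Protocol 1.2 says the randomized phase is meant to show that hyperkalemia returns when ZS is withdrawn. A stop for potassium above 6.2 mmol/L is that return in a severe form, so it is an efficacy failure expected mainly on placebo. Through the reporting rule it can also become an AE withdrawal.

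Readers compare AE withdrawals between arms to judge tolerability. If the placebo count contains relapses and the ZS count contains intolerance, the row measures two different things, and no other planned table shows how much of each it holds. Because the placebo arm is half the size of each ZS arm, one placebo event also moves its percentage twice as far.

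**Working it through.** **1. Arm sizes.** Protocol 8.2 plans 100, 100 and 50 patients, SD 0.50, difference 0.30, two-sided 5%, power >90%. Check: SE = 0.50 × √(1/100 + 1/50) = 0.0866; 0.30/0.0866 = 3.46; power ≈ Φ(3.46 − 1.96) = 93.4% (93.1% with the noncentral t). The stated figure is reproduced. It serves here only to confirm the denominators.

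**2. Which stops are reportable.** The rule needs a worsening from baseline.
- Against the randomization value the condition is always met: entry to the randomized phase requires i-STAT 3.5–5.0 mmol/L, so a stop above 6.2 is a rise of more than 1.2.
- Against the SAP's safety baseline for this phase (3.3.1.1, the last value before the first open-label dose) it is met unless the patient entered at or above the stopping value. Protocol 1.2 sets no upper limit at entry. A patient who entered at 6.5 and stopped at 6.3 would not qualify.
- Protocol 8.2 equates an 18% reduction with 1.05 mmol/L, which implies a planning mean at entry of about 1.05/0.18 = 5.8 mmol/L, below 6.2. This supports most, not each. The share of patients entering above 6.2 is not given.

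**3. Weight of one stop.** Placebo: 1/50 = 2.0 points. Each ZS arm: 1/100 = 1.0 point.

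**4. Range for placebo stops above 6.2.** The documents give no rate; the first column is assumed.

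| Assumed placebo rate | Expected stops in 50 | Points added to placebo row | Chance of at least one, 1 − (1 − p)^50 |
|---|---|---|---|
| 0% | 0 | 0 | 0% |
| 2% | 1 | 2 | 64% |
| 4% | 2 | 4 | 87% |
| 6% | 3 | 6 | 95% |
| 10% | 5 | 10 | >99% |
| 15% | 7.5 | 15 | >99% |

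At 0% there is no mixing. If 0–2% of ZS patients also stop for a value above 6.2 (assumed), their row gains 0–2 points.

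**5. Net direction.** Let *b* be the potassium-criterion stops counted on placebo and *a* those counted on one ZS arm, high and low together. The ZS-minus-placebo difference shifts by a/100 − b/50, which is zero when a = 2b. Examples:
- b = 2, a = 0: −4.0 points
- b = 2, a = 4: 0
- b = 0, a = 2: +2.0 points

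Stops below 3.0 mmol/L would fall mainly on ZS and so belong in *a*. Whether they are counted is unclear, because hypokalemia is not MedDRA-coded. The sign is therefore open.

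**6. Other outputs.** The disposition summary (SAP 4.1.1.1) counts discontinuations and names no reason except the global/country situation. The related-AE table should omit relapses under Appendix A, but it is not limited to withdrawals. Protocol 8.5.3 requires a narrative for every AE leading to withdrawal, and all AEs are listed, so a hand count is possible. None of these is a table by arm of withdrawals split by cause.

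**The case against.** The strongest reply is that little is hidden. Edema is tabulated by arm and phase, hypokalemia by arm at three thresholds, and AEs by preferred term, severity and relatedness. Narratives and listings identify every case. The safety analysis is descriptive, and no test uses this row. The disposition list is also described as not exhaustive, so reasons for stopping could still be added. All of this stands. It limits the point to one summary row and the missing table behind it.

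Three stronger readings are tempting, and the documents do not support them.

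- **A reader might infer that each stop above 6.2 is an AE by rule.** Section 6.3.6 is worded as a restriction and requires worsening from an unnamed baseline. Section 3.9 and the SAP's deviation list (items 3.2 and 3.10) keep the potassium criterion apart from adverse events. Appendix A says how causality is rated when effect is lacking; it does not say that every such stop is recorded as an AE.
- **A reader might put a size on the ZS intolerance being offset.** Protocol 1.3.2 gives edema by arm and says "Fifty-three percent were managed with initiating a diuretic or adjusting a diuretic dose"; section 7.7 says "If clinically indicated to change the RAAS inhibitor and/or diuretics, the patients should discontinue study medication". Multiplying these gives no valid withdrawal rate. The 53% is not reported by arm, and section 3.9 lists a diuretic change as its own stopping reason, so nothing shows that such stops enter the AE row.
- **A reader might infer that the row will conceal or turn round a ZS signal.** That needs a rate of stops above 6.2, which is not given, and it leaves out low-potassium stops and any high-potassium stops on ZS. Protocol 1.1 reports 71% to 85% of ZS patients normokalemic at end of treatment, so ZS relapse cannot be taken as nil.

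**Conclusion.** The point holds as a gap in presentation. Most randomized-phase stops for confirmed potassium above 6.2 mmol/L are reportable as AEs leading to withdrawal, although the SAP treats the same stops as efficacy events. No planned table separates them by arm from withdrawals unrelated to potassium.

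The only firm size is 2.0 points per placebo stop, against 1.0 on a ZS arm. The total and its sign are unknown. The conclusion assumes that few patients enter with potassium above 6.2, or that sites judge worsening against the randomization value. It does not question the stopping rules. This is a cheap improvement that makes the tolerability comparison less dependent on efficacy failure; the primary and secondary efficacy results are not affected.

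**What to change.** In SAP 4.3.2.2:

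1. Tabulate AEs leading to treatment withdrawal by preferred term and arm for the randomized phase.
2. Repeat the withdrawal row without any potassium-criterion stops.
3. Beneath it, show stops for confirmed values above 6.2 and below 3.0 mmol/L on separate lines by arm. Identify them from the recorded i-STAT values and the recorded reason for stopping, because hypokalemia has no MedDRA term in this plan and sites may differ in what they enter as an AE.

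Both directions should be taken out together; removing only the high stops would create a new imbalance. The overall count of patients with any AE needs no second version.

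The cost is a few lines of SAP text and one short descriptive table from data already collected. AE reporting, stopping rules and patient care do not change.
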